Study design. We will conduct a Randomized, 24-week, double-blind study, comparing fluoxetine with aripiprazole in 48 patients with attenuated positive symptoms at a level of at least moderate severity. In choosing the antidepressant and the antipsychotic medication for this trial, we sought medications that had strong available evidence for their efficacy and safety, a high benefit-to-risk ratio, current FDA approval for use in adolescents who will be a core patient group for this study, and a longer half life in order to minimize treatment gaps when doses are taken irregularly. Moreover, since patients in this study will not have suprathreshold psychotic symptoms, choosing an antipsychotic with the least short- and long-term safety concerns was important to increase patient and family acceptability and to be in equipoise about these two intervention strategies. Based on these criteria, we chose fluoxetine over other antidepressant alternatives and aripiprazole over other antipsychotic alternatives.

Inclusion Criteria: 1) consent obtained from patients and their parents (assent for patients under 18); 2) age 12-25 years (inclusive); 3) English-speaking; 4) at least one positive (Scale A) SOPS score of 3-5, i.e., moderate, moderately severe or severe.

Exclusion Criteria: 1) lifetime diagnosis of an Axis I psychotic disorder, including: schizopreniform disorder, schizophrenia, schizoaffective disorder, bipolar disorder, or major depression with psychotic features; 2) current psychosis (any positive symptom SOPS score of 6, i.e., extreme); 3) current diagnosis of Major Depressive Disorder, single episode or recurrent, severe without psychotic features; 4) current stimulant treatment; 5) history of neurological, neuroendocrine or other medical condition known to affect the brain; 6)

any significant medical condition that contra-indicates treatment with either aripiprazole or fluoxetine; 7) past or current substance dependence; substance abuse within the last 4 weeks; 8) IQ < 70.

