Specific Primary Aim 1. *To compare fluoxetine and aripiprazole on time to all-cause-discontinuation/need to add another psychotropic agent, prodromal symptom change and adverse effects in prodromal individuals.* Binary outcomes, such as the primary composite outcome variable and the dichotomized presence of specific side effects (i.e., present=moderate severity or higher) or non-adherence, will be analyzed using chi squared test or Fischer's Exact test, as necessary. Standard methods of survival analysis (Kaplan-Meier product-limit method, logrank test, Cox proportional hazards regression) will be applied to the secondary, time dependent variable "time until all-cause-discontinuation/need to add another psychotropic". If during the trial a subject is lost to follow up, that subject's data will be "censored" at the week of dropout. Cox proportional hazards regression model will be used to determine which factors (if any) are predictive of all cause discontinuation. In addition to the ITT analyses, we will also conduct a sensitivity analysis using only data from subjects as long as they remained on the assigned treatment, censoring data at the week of treatment discontinuation.

Repeated measures analysis of variance (RMANOVA) using a mixed models approach (SAS PROC MIXED, SAS Institute, Cary, NC) will be used to examine the longitudinal and between-drug patterns in continuous outcomes, such as psychopathology rating scores and severity of side effects. In case of relevant missing data, PROC MIXED will be able to model the data despite the missing values. RMANOVA using the mixed models approach will be utilized to analyze changes in weight, BMI and HOMA-IR (using the log ratio transformation). The method of generalized estimating equations (GEE) will be used to analyze ordinal data, such as Barnes and Simpson-Angus scores.

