Specific Secondary Aim. *To compare the effect of fluoxetine and aripiprazole on social and role functioning and subjective well-being in individuals at risk for schizophrenia.* As for primary aim 1, repeated measures analysis of variance (RMANOVA) using a mixed models approach (SAS PROC MIXED, SAS Institute, Cary, NC) will be used to examine the longitudinal and between-drug patterns in these continuous outcomes. In addition, the correlation between social and role functioning scale score changes and changes in attenuated positive and negative symptoms scores will be analyzed using the Bland and Altman methodology. Likewise, correlations between changes in subjective well being and psychopathology scores as well as side effect change scores will be analyzed using that same methodology.

Table 2: Assessment Timetable

Weeks/ Months	Pre-screen	Screen	Wk 0	Wk 1	Wk 2	Wk 3	Wk 4	Wk 6	Wk 8	Wk 12	Wk 16	Wk 20	Wk 24
Assessments													
MD													
Physical Examination		+											
SAFTEE (side effects)			+	+	+	+	+	+	+	+	+	+	+
Psychometrician													
Kid-SCID		+											
Premorbid Adjustment		+											
IQ Test		+											
SIPS/SOPS	+	+	+	+	+	+	+	+	+	+	+	+	+
BPRS, SANSS			+	+	+	+	+	+	+	+	+	+	+
CGI			+	+	+	+	+	+	+	+	+	+	+
Hamilton Scale for Depression			+	+	+	+	+	+	+	+	+	+	+
Young Mania Rating Scale			+	+	+	+	+	+	+	+	+	+	+
Drug Attitude Inventory			+				+		+	+	+		+
Social Functioning and Role Functioning Scale			+							+			+
Subjective Wellbeing Scale (SWN-K, Naber 1995)			+							+			+
Research Technician													
Simpson-Angus (EPS)			+	+	+	+	+	+	+	+	+	+	+
Barnes Akathisia			+	+	+	+	+	+	+	+	+	+	+
AIMS (Dyskinesia)			+	+	+	+	+	+	+	+	+	+	+
Vital signs/Weight			+	+	+	+	+	+	+	+	+	+	+
Fasting blood tests (CBC, comprehensive metabolic panel, glucose, insulin, lipid profile, TSH, LFTs) and urine analysis		+ ^a	+					+		+			+
Study medication level									+		+	+	
Pregnancy test (urine ^d or serum)			+	+				+		+	+		+
Urine toxicology			+	+				+		+	+		+
DNA blood draw & storage (optional)				+ ^b									
Brain Derived Neurotrophic Factor			+	+				+		+	+		+

^a can be non-fasting, no insulin and lipid level required; ^b can be obtained at any time during the study if needed; ^c SIPS can be used from Pre-screen if screening done within 2 days.

^d when subject outpatient, urine test will be used, when inpatient then we will use serum pregnancy test already for in unit.

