Exploratory Aim. To compare the effect of fluoxetine and aripiprazole on BDNF levels to determine potentially beneficial neurotrophic effects that mediate symptomatic and/or functional benefits. Similar statistical methods as for the continuous outcomes in aim 1 and aim2 will be used.

Power Calculations and Sample Size. This is a pilot study with the aim to assess the feasibility of this design for a larger trial and to obtain preliminary data that would guide future power and effect size analyses. For the purposes of this trial, we used an estimate of a 40% difference between the two treatments on the combined primary outcome of all-cause-discontinuation and need for addition of another major psychiatric medication. Based on preliminary data, we estimated the rates to be 65% with antipsychotics and 25% with antidepressants. With 24 subjects in each treatment arm, we will have 82% power to find a statistical difference in the primary composite outcome in a two tailed t-tests with alpha <.05 (online calculator used for this power/sample size calculation: <http://www.stat.ubc.ca/~rollin/stats/ssize/b2.html>). This is a conservative estimate, as repeated

measures ANOVA will yield greater power, compensating for any drop outs prior to the first post-baseline assessment.

HUMAN SUBJECTS

This human subjects research meets the definition for clinical research.

Protection of Human Subjects

1. Risks to the Subjects

Fluoxetine is approved by the Food and Drug Administration (FDA) for the treatment of depression, obsessive-compulsive disorder (OCD), and panic disorder in adults and for depression, anxiety and OCD in children and adolescents. Aripiprazole is approved by the FDA for the treatment of schizophrenia and bipolar disorder in adults and in children and adolescents age 10-17 (bipolar disorder) and age 13-17 (schizophrenia). Neither medication is specifically indicated in adolescents for the symptoms for which they are prescribed in this trial. However, both medications are widely used for a range of disorders in children and adolescents, and both have been used successfully in the RAP Program. This study includes detailed procedures for safety monitoring.

These procedures are outlined below.

There are a number of common, non-serious side effects associated with use of [fluoxetine](#): nausea, diarrhea, intestinal discomfort, headache, insomnia, sexual side effects, dry mouth, fatigue/drowsiness and dizziness.

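### The plan names no baseline covariate for any continuous outcome, which gives up precision on secondary and exploratory comparisons where the baseline-to-Week-24 correlation is moderate

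*Combined protocol and SAP*

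**What the plan says.** Under Analytic Plan, Specific Primary Aim 1, a repeated-measures ANOVA fitted in PROC MIXED "will be used to examine the longitudinal and between-drug patterns in continuous outcomes, such as psychopathology rating scores and severity of side effects". The same paragraph adds that "RMANOVA using the mixed models approach will be utilized to analyze changes in weight, BMI and HOMA-IR (using the log ratio transformation"). A log ratio is a change on the log scale. The wording leaves open whether it applies to HOMA-IR alone or to all three measures.

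Under Specific Secondary Aim, the same method "will be used to examine the longitudinal and between-drug patterns in these continuous outcomes", meaning social and role functioning and subjective well-being. For BDNF, the Exploratory Aim says "Similar statistical methods as for the continuous outcomes in aim 1 and aim2 will be used".

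None of these paragraphs lists fixed effects, a covariance structure or a target contrast. None says whether Week 0 belongs to the response vector, or whether the arms share a mean there. Predictors are mentioned only for the Cox model of discontinuation. Table 2 marks Week 0 for SIPS/SOPS, BPRS, the Hamilton and Young scales, functioning, well-being, weight, fasting bloods and BDNF, so the baseline values will exist.

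**The concern.** In a randomised comparison, the Week 0 value of an outcome is usually the best single predictor of its later value. Analysing change subtracts that value with a coefficient fixed at 1. Adjusting for it uses the estimated coefficient, which is smaller when the correlation is below 1, and so leaves less noise.

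Calling the model mixed does not settle the matter. If Week 0 is one of the responses and the arm-by-visit means are unconstrained, the Week 24 contrast with complete data is simply the difference in mean change.

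Several named hypotheses rest on these models: similar change in psychopathology, better functioning, greater well-being and a larger BDNF increase. A claim of similarity depends on interval width in particular. The trial is also a pilot meant to inform later effect-size work, so the precision of these estimates is part of what it delivers. With 24 per arm, chance baseline differences are to be expected on some scales, and a change score passes part of each difference into the result.

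**Working it through.** **Inputs from the plan.** The design is "comparing fluoxetine with aripiprazole in 48 patients with attenuated positive symptoms at a level of at least moderate severity". Under Power Calculations: "With 24 subjects in each treatment arm, we will have 82% power to find a statistical difference", with "two tailed t-tests with alpha <.05" and, for the binary composite, "we estimated the rates to be 65% with antipsychotics and 25% with antidepressants".

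**Inputs assumed.** The documents give no SD, effect size or baseline-to-follow-up correlation (rho) for any continuous outcome. I take equal SDs at both visits (SD = 1), rho from 0.3 to 0.95, complete data on 48 patients, and for illustration a difference of 0.6 SD.

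**Step 1: the plan's own figure.** For 65% against 25% with n = 24 per arm, the mean rate is 0.45.
- Null SE = sqrt(2 × 0.45 × 0.55 / 24) = 0.1436.
- Alternative SE = sqrt((0.65 × 0.35 + 0.25 × 0.75) / 24) = 0.1315.
- z = (0.40 − 1.96 × 0.1436) / 0.1315 = 0.90, so power is 81.6%.

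This reproduces the stated 82%. It concerns only the binary primary outcome and uses no baseline value.

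**Step 2: variance formulas.** Per-patient variance is 2(1 − rho) for change and 1 − rho² after baseline adjustment. The ratio is (1 + rho)/2.

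**Step 3: cost of estimating the slope.** The formula in Step 2 is a large-sample one. With 48 patients, the adjusted variance is inflated by about 1 + 1/44. A simulation of 20,000 trials per rho at 24 per arm includes this cost directly.

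| rho | change | adjusted | ratio, formula | ratio, simulated | SE reduction (simulated) | 48 / simulated ratio |
|---|---|---|---|---|---|---|
| 0.3 | 1.40 | 0.91 | 0.65 | 0.68 | 18% | 71 |
| 0.5 | 1.00 | 0.75 | 0.75 | 0.77 | 12% | 62 |
| 0.7 | 0.60 | 0.51 | 0.85 | 0.87 | 7% | 55 |
| 0.9 | 0.20 | 0.19 | 0.95 | 0.97 | 1.5% | 49 |

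The SE reduction is 1 − sqrt(simulated ratio). The last column is the number of patients a change analysis would need to match the adjusted analysis of 48. At rho = 0.95 the formula ratio is 0.975, and 0.975 × (1 + 1/44) = 0.997, so there the gain is essentially nil.

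**Step 4: power for an assumed 0.6 SD difference.** These are two-sided t-based figures, with SE = sqrt(variance × 2/24) and 46 df for change or 45 for the adjusted analysis.
- rho 0.3: 40.5% for change, 56.8% adjusted.
- rho 0.5: 53.0% for change, 65.1% adjusted.
- rho 0.7: 74.8% for change, 81.3% adjusted.

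Multiplying the adjusted variance by 1 + 1/44 lowers each adjusted figure by about one point, to 56%, 64% and 80%.

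**Step 5: chance imbalance.** One SE of baseline difference between arms is sqrt(2/24) = 0.29 SD. Given a baseline difference d, the change contrast is shifted by −(1 − rho)d. At rho = 0.5 that is 0.5 × 0.29 = 0.14 SD. Baseline adjustment removes this shift on average.

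**The case against.** The strongest reply is that the plan is silent rather than wrong. It lists no model terms, so nothing excludes a baseline covariate, and a PROC MIXED model with equal arm means at Week 0 fits the text and would recover essentially the whole gain. This stands: a reader might infer that the plan rejects baseline adjustment, and the documents do not support that. It does not remove the point, because the metabolic outcomes are expressly analysed as changes and the other models leave the handling of Week 0 open.

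The size is also open to challenge. Rho and the 0.6 SD difference are both assumptions. The plan never names Week 24 as the contrast. For psychopathology the hypothesis is similarity, so power to detect a difference is not the relevant measure there; interval width is. Weight and BMI, which the plan explicitly analyses as change, may be the weakest examples, because a correlation of 0.9 or more over 24 weeks would leave almost nothing to gain. All of this stands and limits the claim.

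The remedy is not free either. A model of post-baseline values drops treated patients who have no post-baseline visit. The plan's analysis set is everyone randomised who took a dose, and its power section foresees dropout before the first post-baseline assessment. For scales with ten post-baseline visits, drug-by-visit (20 parameters) plus Week 0-by-visit (10) makes 30 fixed effects. An unstructured covariance would add 10 × 11 / 2 = 55 more, all on 48 patients.

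**Conclusion.** The point holds as a worthwhile improvement to the secondary and exploratory analyses. No baseline covariate is named for any continuous outcome, the Week 0 values are collected, and without a constraint of equal arm means at Week 0 the Week 24 comparison has change-score precision.

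The size depends on a correlation that the documents do not give. Standard errors fall by roughly 7% to 18% for rho between 0.7 and 0.3, by about 1.5% at 0.9, and hardly at all near 0.95. Moderate correlation is more plausible for symptom scales, functioning, HOMA-IR and BDNF than for weight and BMI, but that too is an assumption. The power figures further assume a 0.6 SD difference and complete data.

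Two stronger readings are tempting, and the documents support neither. One is that the change-score comparisons are invalid: under randomisation they remain unbiased and are only less precise. The other is that the trial's stated power is affected: the 82% refers to the binary composite, it reproduces, and baseline adjustment of continuous outcomes neither lowers nor raises it.

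**What to change.** State the PROC MIXED model for all continuous outcomes, including BDNF, before unblinding. Either of two forms would do:

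- Keep Week 0 in the response vector with visit and drug-by-visit terms, constraining the arm means to be equal at Week 0. This retains all treated patients, including those with only a Week 0 value, and fits the plan's analysis set better.
- Model the post-baseline values with drug, visit, drug-by-visit and the outcome's Week 0 value, adding Week 0-by-visit where the number of visits allows it. Patients without a post-baseline value then do not contribute.

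In both forms, analyse HOMA-IR on the log scale, including its Week 0 value, and say whether weight and BMI are also logged. Name the drug difference at Week 24, with its confidence interval, as the reported contrast.

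The cost is a short paragraph in the Analytic Plan and a few extra model parameters. It needs no additional patients, visits or assays. Settling it in advance also prevents a later choice between adjusted and unadjusted results.

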While these first findings of a protective effect of antidepressants in prodromal individuals add to an intriguing line of primarily indirect evidence suggesting that antidepressants, which have a favorable risk-benefit ratio, may influence the development of psychosis, the lack of randomization and potential of prescriber bias reduce the interpretability of these early data. Therefore, we now propose to conduct a randomized, controlled 6-month pilot study comparing the antidepressant fluoxetine with the second generation antipsychotic aripiprazole in 48 subjects aged 12-25 years with at least moderate attenuated positive symptoms that developed within the past five years. Since transition to psychosis can occur at a relatively low rate over a very variable and potentially long time frame, and since discontinuation rates in long-term studies of putatively prodromal cohorts have been very high, we have designed a randomized, double-blind study focusing on intermediate outcomes, including the composite of all-cause-discontinuation and/or addition of a major psychotropic medication (see below), symptom change, safety, and adherence. The specific aims are:

Specific Primary Aim 1: To compare fluoxetine and aripiprazole on the likelihood of and time to all-cause discontinuation/need to add another psychiatric medication, symptomatic improvement, and adverse effects

Primary Hypothesis 1: Compared to aripiprazole, significantly fewer patients on fluoxetine will either discontinue treatment or require the addition of an antipsychotic, mood stabilizer, antidepressant or of >3 weeks of treatment with an anxiolytic/hypnotic

Secondary Hypothesis 1: Compared to aripiprazole, time to all-cause discontinuation or need to add another psychiatric medication (as defined above) will be significantly longer with fluoxetine

Secondary Hypothesis 2: Compared to aripiprazole, changes in attenuated positive, negative and general psychopathology will be similar with fluoxetine.

Secondary Hypothesis 3: Compared to aripiprazole, fluoxetine will be associated with significantly lower rates of adverse effects.

Specific Secondary Aim 1: To compare the effect of fluoxetine and aripiprazole on social and role functioning and subjective well-being in individuals at risk for schizophrenia.

Primary Hypothesis 1: Compared to aripiprazole, fluoxetine will lead to significantly greater improvement in social and role functioning.

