Recruitment. We will recruit patients utilizing the ACISR Trials Operation Unit, which has developed recruitment strategies within the child and adolescent as well as adult outpatient and emergency room services at Zucker Hillside Hospital, with additional referrals from the inpatient units. In addition, to increase the pool of potentially eligible patients, our ACISR maintains a Research Network that will liaise with local community mental health clinics offering a screening program for potentially prodromal symptoms in the clinic clientele. We will approach mental health clinics associated with Queens Child Guidance Center (5 clinics), North Shore Child Guidance Center (3 clinics), South Shore Child Guidance Center, Peninsula Counseling Center, Pederson-Krag Center, as well as the outpatient clinics of Kings County Hospital and Stony Brook Hospital. Finally, we are setting up a collaboration with the St Luke's Roosevelt hospital PEER program in Manhattan, a dedicated first episode and prodromal psychosis outpatient program that just received 2-year structural funding from the van Ammeringen Foundation. Furthermore, we are in contact with the psychiatry department at SUNY Downstate. St. Luke's Roosevelt and, potentially SUNY Downstate, will become sites for this study and will need to obtain their own IRB approval. The other mental health clinics will be utilized as referral sources. Thus, while presentations and outreach will take place, patients will not be assessed and treated at these centers; treatment will reside at the treatment sites, namely Zucker Hillside Hospital, St. Luke's Medical Center and, possibly SUNY Downstate.

Medication Schedule. Randomization codes to either aripiprazole or fluoxetine will be provided by the NSLIJ biostatistics group. To increase homogeneity and assure treatment with a clinically effective dose, patients will undergo a fixed titration phase during the first three weeks, with the option to slow or halt the titration or

Table 1. Titration	Wk 0/Wk 1	Wk 1/2	Wk 2/3	Week 4-Week 24
	Fixed	Fixed	Fixed	Flexible Dosing, Range
Fluoxetine	10 mg	10 mg	20 mg	10mg – 60mg
Aripiprazole	2 mg	5 mg	10 mg	5mg – 30mg

decrease the target dose if intolerance develops (Table 1). After 3 weeks, dosing will be flexible and left up to clinical choice and need.

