the predetermined time points independent of whether they are compliant with the study protocol to allow for an ITT analysis. The primary outcome variable for this project will be discontinuation of medication or addition, as verified by prescription, of another psychotropic medication to the daily treatment regimen of the subject (excluding prn medications). Patients that are not compliant at least 80% of the time will be subject to an unscheduled study termination.

Optional Genetic Test Component

Once during the study period, each subject will be asked to provide an additional 16 ml blood sample (approximately 1 tablespoon) for DNA collection and genotyping. The collected blood samples will be stored in locked freezers. Blood samples will be transferred to the Feinstein Institute for Medical Research ([name] lab) Human Genetics Program core facility for lymphocyte extraction. From this lymphocyte extraction, 50% will be used for direct DNA extraction and 50% will be utilized to establish Epstein-Barr virus-transformed cell lines. We will store the DNA for future exploratory analyses comparing patients with conversion to psychosis or worsening of prepsychotic symptomatology to those patients who did not worsen or convert. These exploratory analyses will target potentially relevant genomic regions involved in schizophrenia and genomic regions involved in conversion to psychosis potentially identified by then in other prodromal research cohorts.

Analytic Plan

General Considerations. All analyses will be conducted in an ITT sample using all randomized patients who received at least one dose of medication. Although the analytic methods to be described below (i.e. survival analysis, mixed models, RMANOVA, etc.) are fairly routine, missing data can cause problems in the statistical analyses. Thus, if the necessary, we will consider the use of multiple imputation techniques (i.e., PROC MI and PROC MIANALYZE), using the assumption of data being "missing at random" (MAR). In this case, we will transform non-monotone missing data patterns to monotone patterns, which are easier to analyze.

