a. Recruitment and informed consent

For each potentially eligible patient, a parent (or guardian) will be contacted by the treating physician to obtain permission to be contacted for participation in a research study. Following this permission, the treating physician, Co-I, or clinical psychologist affiliated with the study will discuss the study with the caregiver and the patient. Each parent will receive a complete explanation of the purposes, duration, procedures, and potential risks and benefits of this study. A similar explanation will be given to the child, commensurate with his/her age and ability to comprehend. Any questions that the family may have will be answered. If the family agrees to participate, written informed consent will be obtained from the parents and written assent from the child. A copy of the signed consent form will be placed in the child's medical record. Parents will be informed that both aripiprazole and fluoxetine are currently marketed medications, which can be prescribed by their physician for their child without study participation. The right of the family to withdraw the child from the study at any time will be made clear. Typically, several meetings with patients and family members will be devoted to the consent process. Because the study involves pharmacological interventions, a child and adolescent psychiatrist will always be involved in obtaining consent.

b. Protection against risk

The proposed medications are not experimental agents, but are being used widely in children and adolescents in general clinical practice. Participation in the proposed study will mean that patients will undergo regular, frequent careful assessments of adverse effect and of efficacy as outlined in table 2. This is a more rigorous assessment of risks and benefits than usually provided as part of general psychiatric community care. Moreover, the study will use predefined exit rules, such as a CGI-I score of much or very much worse or a 20% worsening on the BPRS scale, further protecting against risk from not benefiting from study participation.

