To screen for and guard against suicidal ideation and suicidal behavior, the suicidality item in the HAM-D will be used as a screening tool. If any symptoms are rated greater than zero, this will be followed by a formal assessment with the Columbia-Suicide Severity Rating Scale (Mundt et al. 2010), and appropriate clinical steps will be initiated as needed. Additionally, for patients in whom weight gain of $\geq 7\%$ is detected throughout the trial, healthy lifestyle interventions involving simple education regarding diet and physical activity will be implemented. If weight gain continues and exceeds 10% over baseline body weight, the subject may be withdrawn from the study or metformin can be offered as per clinical need while continuing in the study.

3. Potential of Benefits of the Proposed Research to the Subjects and Others

The patients who will be selected for inclusion in this study will be adolescents and young adults with symptoms and signs that fulfill criteria for the psychosis prodrome. No benefit can be promised to the study participant, him/herself, although the medication treatment in each arm can be expected to alleviate often impairing and/or distressing symptoms and signs consistent with a psychosis prodrome. Moreover, patients will benefit from close observation during the study. The blind for each study subject will be broken after all study data has been collected for that individual. The information about the response of the subject may be helpful for treatment planning.

4. Participant Compensation

Participants will be paid \$30 for each of the 6 longer visits, ie, at screening and weeks 0, 4, 8, 12 and 24 (\$180), and \$20 for each of the 6 short visits at weeks, 1, 2, 3, 6, 16, and 20 (\$120). Thus, total maximum compensation for complete participation in all 12 visits of this randomized controlled study will be \$300 per participating family. If a participant withdraws before the study is completed, they will be paid for their participation up to that time. Compensation will be provided as check or cash after each reimbursable study visit with instructions that it is intended to support the entire family's expenses associated with the assessment. In addition, parking or public transportation costs will be reimbursed or transportation may be provided. Light, healthy meals or meal vouchers will be provided after fasting labs are obtained.

5. Importance of the Knowledge to be Gained

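### Each participant's blind is broken as soon as that participant's data are complete, with no limit on who is told, while others are probably still being treated and rated

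*Combined protocol and SAP*

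**What the plan says.** The unblinding rule appears once, in Human Subjects, section 3 (Potential of Benefits): "The blind for each study subject will be broken after all study data has been collected for that individual". The next sentence gives the purpose: "The information about the response of the subject may be helpful for treatment planning". No recipient is named. No other section ties release to the last patient's final visit or to database lock, or keeps unblinded staff away from patients still enrolled.

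The Specific Aims say "we have designed a randomized, double-blind study focusing on intermediate outcomes", and Study design repeats the label: "Randomized, 24-week, double-blind study, comparing fluoxetine with aripiprazole in 48 patients".

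The Assessments text defines the endpoint: "The primary outcome variable for this project will be discontinuation of medication or addition, as verified by prescription, of another psychotropic medication". Several provisions give clinicians influence over it:
- Medication Schedule: "After 3 weeks, dosing will be flexible and left up to clinical choice and need".
- Protection against risk: "the study will use predefined exit rules, such as a CGI-I score of much or very much worse", or a 20% worsening on the BPRS.
- The suicidality and weight-gain paragraph leaves withdrawal as an option once weight gain exceeds 10%.

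Other provisions give influence to patients. Families may withdraw at any time, and adherence below 80% leads to termination.

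Table 2 divides the ratings. SAFTEE is listed under the MD. SIPS/SOPS, BPRS and CGI are under the psychometrician. The Simpson-Angus, Barnes and AIMS scales are under the research technician.

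Randomization codes come from the biostatistics group. Blocking, block size and stratification are not stated, and neither is the accrual period.

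**The concern.** A double-blind trial normally keeps every allocation masked until all outcomes are in. Here release is patient by patient, and its stated use is treatment planning, so clinicians are the natural recipients. A finished patient's own data are safe, because they are complete before the code is opened. The exposure falls on patients who have not finished.

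There are two routes to it. The first is learning. The protocol lists partly different side effects for the two drugs: extrapyramidal symptoms, restlessness and weight change for aripiprazole, and diarrhea and insomnia for fluoxetine. Each opened code tells staff whether their guess was right. The second is deduction, which works only if allocation was in permuted blocks.

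At stake are decisions to stop or add medication, and the symptom and side-effect ratings behind the secondary hypotheses. The hypotheses favour fluoxetine on the primary outcome, functioning and adverse effects, so expectation has a direction. Later analysis could not remove such a bias.

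**Working it through.** **1. The plan's own figure.** Inputs from Power Calculations and Sample Size: 65% versus 25%, 24 per arm, two-sided 0.05. With pooled variance under the null and a mean rate of 0.45:

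z = [0.40 − 1.96 × √(2 × 0.45 × 0.55 / 24)] / √[(0.65 × 0.35 + 0.25 × 0.75) / 24] = (0.40 − 1.96 × 0.1436) / 0.1315 = 0.901

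This gives 81.6% power, against 82% stated. The timing of unblinding does not enter the calculation.

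**2. How much of the trial follows the first unblinding.** The accrual period is assumed, with even entry of 48 patients and the first code opened at week 24.

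| Accrual (weeks) | Others on treatment at first unblinding | Not yet enrolled | Treatment time after it |
|---|---|---|---|
| 26 | 43 | 4 | 54% |
| 52 | 21 | 26 | 76% |
| 104 | 10 | 37 | 88% |
| 156 | 7 | 40 | 91% |

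Random (Poisson) entry at an assumed 1 to 2 patients per month gives 86% to 92%. Under every assumption, at least half of treatment time follows the first opened code.

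**3. Deduction, if blocks were used (assumed).** If every earlier allocation in a block of size B were known, the expected share fixed with certainty is 1/(B/2 + 1). That is 50%, 33%, 25% and 20% for B = 2, 4, 6 and 8. In practice block-mates overlap in time. Simulation with one site, 1 to 2 entries per month and blocks of 4 or 6 finds that 33% or 25% of patients become deducible before they finish, but only for 11% to 25% of their treatment time. That is about 3% (0.25 × 0.11) to 8% (0.33 × 0.25) of all treatment time.

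**4. What one-arm bias would do to the test.** Exact rejection probability with 24 per arm, no true difference and a 45% rate, when k extra events are added in one arm (45% versus 45% + k/24):

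| k | Rates | Chi-squared | Fisher |
|---|---|---|---|
| 0 | 45.0% v 45.0% | 5.8% | 2.9% |
| 1 | 45.0% v 49.2% | 7.0% | 3.6% |
| 2 | 45.0% v 53.3% | 10.2% | 5.7% |
| 3 | 45.0% v 57.5% | 15.7% | 9.5% |

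Both tests are shown because the Analytic Plan allows either.

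**5. Steps 3 and 4 do not join up.** With a constant hazard and a 45% event rate over 24 weeks, take the larger share in step 3: one third of 24 is 8 patients per arm. Events expected in the deducible window are 8 × (0.55^0.89 − 0.55) = 8 × 0.037 = 0.3 for an 11% window, and 8 × (0.55^0.75 − 0.55) = 8 × 0.089 = 0.7 for a 25% window. Deduction under these assumptions therefore gives no basis for k = 2 or 3. The values of k illustrate how sensitive the test is. They do not estimate the bias.

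**The case against.** The strongest reply is that the rule opens only finished patients' codes, and that staff can guess from side effects under any schedule. Weight gain, akathisia, or adjunctive benztropine or propranolol are visible hints whether or not codes are opened. This stands: delayed release would remove only the increment, which is confirmed feedback plus any deduction from blocks. That increment has no benefit that must be obtained this way.

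Four stronger readings are tempting, and the documents do not support them.
- *The people who decide the endpoint also make all the ratings.* Table 2 puts only SAFTEE with the MD. The psychometrician's CGI and BPRS ratings reach the primary outcome only through the exit rules.
- *Staff alone decide the primary outcome.* Family withdrawal and non-adherence also produce events, and additions must be verified by prescription.
- *A quarter to a third of patients will have their allocation deduced.* Blocking is never stated, and the figure assumes one site, whereas Recruitment plans a second and possibly a third. With blocks stratified by site (assumed), simulation gives 22% to 32% of patients, for 22% to 55% of their time. The answer follows the assumptions.
- *The true false-positive rate is 7% to 16%.* Those values follow from chosen numbers of extra events, and Fisher's test gives lower ones.

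It is also fair to say that this is a 48-patient pilot, and that telling participants which drug they took has real value for their later care.

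**Conclusion.** The point holds as an avoidable weakness in the blinding. The rule is explicit, it is not limited to particular recipients, and if followed as written it would reveal allocations while other patients are still being treated and rated. That last step rests on staggered entry. The documents do not state it, but it follows from recruiting 48 patients through outpatient, emergency and referral services under any realistic schedule.

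The documents do not allow the size of the bias to be estimated. They do show exposure, since at least about half of treatment time falls after the first opened code under the accrual assumptions tried. The endpoint test is also sensitive: with chi-squared, two extra events in one arm would nearly double the false-positive rate, from 5.8% to 10.2%. Nothing in the plan shows that shifts of that size would occur. This is a worthwhile, inexpensive improvement. It does not show that the trial's result would be invalid.

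**What to change.** Replace the sentence in section 3 with a rule along these lines:

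- Allocations are released only after the last patient's Week 24 data are collected and the database is locked.
- If a finished participant's allocation is needed sooner for treatment planning, someone with no role in treating or rating current participants releases it to the participant's later clinician and logs the release. The biostatistics group that provides the codes is one candidate.
- The allocation is not given to staff who still treat or rate enrolled participants. Treatment takes place at the study sites, so the later clinician may be such a person. In that case release waits for database lock, or goes to a clinician not involved in the trial.

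The cost is a short change to the protocol, and to the consent form if it makes the same promise. Some participants and study doctors would learn the allocation later. The sample size stays at 48 and planned power at 82% as stated (81.6% recomputed).
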